2.1.4.2 Deaths

The deaths observation period is per the observation periods defined above.

- Death on-study: deaths occurring during the on-study observation period
- Death on-treatment: deaths occurring during the treatment-emergent adverse event period
- Death poststudy: deaths occurring after the end of the study

2.1.4.3 Laboratory safety variables

Clinical laboratory data consists of blood analysis, including hematology, clinical chemistry, and urinalysis including cotinine. Clinical laboratory values after conversion will be analyzed into standard international units and international units will be used in all listings and tables.

Blood samples for clinical laboratories will be taken at Visit 1 (Week -4±1), Visit 2 (Week 0), Visit 4 (Week 4), Visit 5 (Week 8), Visit 6 (Week 12), Visit 9 (Week 24), Visit 12 (Week 36), Visit 16 (Week 52), Visit 19 (Week 64) and early termination unless otherwise specified. The laboratory parameters will be classified as follows:

- Hematology
 - **Red blood cells and platelets and coagulation:** hemoglobin, hematocrit, red blood cell count, platelet count
 - **White blood cells:** white blood cell count, differential count
- Clinical chemistry
 - **Metabolism:** glucose, total cholesterol, total protein, creatine phosphokinase
 - **Electrolytes:** sodium, potassium, chloride, bicarbonate
 - **Renal function:** creatinine, blood urea nitrogen, uric acid
 - **Liver function:** alanine aminotransferase, aspartate aminotransferase, alkaline phosphatase, lactate dehydrogenase, total bilirubin (in case of values above the normal range, differentiation in conjugated and non-conjugated bilirubin), albumin
 - **Pregnancy test:** Serum β -human chorionic gonadotropin (all female patients) will be performed at screening (V1) in women of childbearing potential, and a urine pregnancy test will be performed at V2 prior to randomization and every 4 weeks thereafter. A negative result must be obtained at V1 and V2 prior to randomization. In case of positive urinary test the study treatment will be withheld and a serum pregnancy test to confirm the pregnancy should be performed as soon as possible. Pregnancy will lead to definitive treatment discontinuation in all cases.
 - **Hepatitis screen:** hepatitis B surface antigen (HBs Ag), hepatitis B Surface antibody (HBs Ab), hepatitis B core antibody (HBc Ab), hepatitis C virus antibodies (HCV Ab) will be tested at screening (V1). In case of results showing HBs Ag (negative), HBs Ab (negative) and HBc Ab (positive), an HBV DNA testing will be performed prior to randomization to rule out a false positivity if the investigator believes the patient is a false positive, or to clarify the serological status if the investigator finds it unclear to interpret in absence of known HBV infection. In case of results showing HCV Ab (positive), an HCV RNA testing may be performed to rule out a false positivity, if the investigator believes the patient is a false positive.

- **HIV screen:** Anti-HIV-1 and HIV-2 antibodies will be tested at Visit 1
- **Anti-nuclear antibody (ANA)** will be tested at Visit 1
- Note: Anti-ds DNA antibody will be tested if ANA is positive ($\geq 1:160$ titer).
- **Urinalysis**
Urinalysis will include specific gravity, pH, glucose, ketones, blood, protein, nitrate, leukocyte esterase, urobilinogen and bilirubin. If any parameter on the dipstick is abnormal, a urine sample should be sent to the central laboratory for quantitative measurement. If positive for protein and/or red blood cells, microscopic analysis will be performed by the central laboratory.

Technical formulas are described in [Section 2.5.1](#).

2.1.4.4 Vital signs variables

Vital signs, including blood pressure (mmHg), pulse rate (beats per minute), respiratory rate (breaths per minute), body temperature (degrees Celsius) will be measured at Visit 1 (Week -4 ± 1), Visit 2 (Week 0), Visit 3 (Week 2), Visit 4 (Week 4), Visit 5 (Week 8), Visit 6 (Week 12), Visit 9 (Week 24), Visit 12 (Week 36), Visit 14 (Week 44), Visit 16 (Week 52), and Visit 19 (Week 64). Height (cm) will be measured at screening (Visit 1) only. Body weight (kg) will be measured at screening (Visit 1) and at EOT/EOS visits. Vital signs will be measured in the sitting position using the same arm (preferably) at each visit and will be measured prior to receiving IMP at the clinic visits.

2.1.4.5 Electrocardiogram variables

A standard 12-lead electrocardiogram (ECG) will be performed centrally at Visit 1 (Week -4 ± 1), Visit 2 (Week 0), Visit 6 (Week 12), Visit 9 (Week 24), Visit 12 (Week 36), Visit 16 (Week 52), and Visit 19 (Week 64). At the post randomization visits, ECGs will be performed prior to investigational product administration. A minimum of 3 complexes in an appropriate lead (lead II) will be averaged to determine the PR-interval, QT/QTc-interval, QRS-complex and heart rate will be measured for each ECG. All ECG recordings will be centrally read by independent experts.

2.1.4.6 Physical Examination

Physical examinations will be performed at Visit 1 (Week -4 ± 1), Visit 2 (Week 0), Visit 9 (Week 24), Visit 16 (Week 52), and Visit 19 (Week 64) including an assessment of skin, nasal cavities, eyes, ears, respiratory, cardiovascular, gastrointestinal, neurological, lymphatic, and musculoskeletal systems. All deviations from normal will be recorded, including those attributable to the patient's disease.

2.1.5 Pharmacokinetic variables

Predose serum dupilumab concentrations at Visit 2 (Day 1), dupilumab trough levels at Week 2, Week 4, Week 8, Week 12, Week 24, Week 36, Week 52/EOT Visit and posttreatment serum dupilumab at Week 64/EOS Visit will be provided.

Anti-dupilumab antibody (ADA) status (negative or titer value, if positive in the ADA assay) at Visit 2 (Day 1), Week 12, Week 24, Week 52 and follow up at Week 64 will be provided. Patients who discontinue early from treatment may be asked to return to the clinic to have additional ADA samples collected for analysis based on the overall clinical presentation at that time.

ADA incidence will be classified as the following:

Pre-existing immunoreactivities are defined as:

An ADA positive response in the assay at baseline with all post treatment ADA results negative, OR an ADA positive response at baseline with all post treatment ADA responses less than 4-fold over baseline titer levels.

Treatment-emergent anti-drug antibodies are defined as:

A positive response in the ADA assay post first dose, when baseline results are negative or missing.

Treatment-emergent ADA responses are further classified as Persistent, Indeterminate or Transient

- a) Persistent Response- defined as a treatment-emergent ADA response with two or more consecutive ADA positive sampling time points, separated by greater than ($>$) 12-week period (84 days), with no ADA negative samples in between.
- b) Indeterminate Response- defined as a treatment-emergent response with only the last collected sample positive in the ADA assay
- c) Transient Response - defined as a treatment-emergent response that is not considered persistent OR indeterminate

Treatment-boosted response is defined as:

An ADA positive response in the assay post first dose that is greater-than or equal to 4-fold over baseline titer levels, when baseline results are positive.

Titer values (Titer value category)

- Low (Titer < 1000)
- Moderate ($1000 \leq \text{Titer} \leq 10\,000$)
- High ($\text{Titer} > 10\,000$)

On-treatment ADA incidence will also be derived in the same way except that only on-treatment measurements (measurements during the treatment epoch) are considered post first dose.

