- a Randomization/baseline visit is defined as Day 1. The visit schedule should be adhered to within ±1 week for the 4-week screening period, ±3 days for the randomized IMP treatment period and ±5 days for the post IMP treatment period. If more than 12 weeks since last on-site scheduled visit, then unscheduled visit is required within 3 weeks of missed scheduled visit (eg, if missed scheduled visit at Week 24, then unscheduled visit must be performed by Week 27; If missed scheduled visit at Week 36, then unscheduled must be performed by Week 39). All the assessments of the missed scheduled on-site visit will need to be carried out at the unscheduled visit.
- b All assessments at Visit 2 (Day 1) are to be conducted pre-IMP dose with the exception of the assessment of local tolerability of SC injections.
- c End-of-treatment visit: See Section 7.1.1 for patients who discontinue treatment prematurely.
- d ECG to be centrally collected & read.
- Chest X-ray to be performed unless a <6-month-old chest x-ray/chest CT/chest MR is available. In case chest-X-ray is not feasible due to local regulations, magnetic resonance imaging (MRI) will be performed.
- f IMP (Dupilumab or placebo) is to be administered every 2 weeks by patient, caregiver or healthcare professional at the patient's home or in a health care facility. Last dose will be given at Week 50. If the patient or Investigator decides not to administer IMP at home, the IMP injections can be performed at the site by way of unscheduled visits. The IMP can be administered at home after training and at least 1 IMP injection at the site and supervised by the Investigator. Patients will be monitored at the study site for a minimum of 30 minutes after injections. See Section 6.1.1 for details. If the patient is unable or unwilling to administer IMP at home, injections can be performed at the site; or arrangements can be made for qualified site personnel and/or health care professionals (eg, visiting nurse service) to administer IMP for the doses that are not scheduled to be given at the study site.

Amended Clinical Trial Protocol 03 EFC15805 - dupilumab

28-Oct-2023 Version number: 1

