For the pharmacokinetics/pharmacodynamics variables summary, the reference date for the derivation of relative days of measurements will be the date of first IMP administration if the patient is treated with study treatment, or the randomization date if the patient is not treated. Pharmacokinetics /pharmacodynamics variables will be summarized by the analysis window defined in [Table 8](#) for the by visit descriptive analyses. All available values of measurements will be assigned to the appropriate visit window. In the event of multiple measurements of the same test in the same window, the one closest to the targeted visit date will be used for the by-visit summary. If they are at the same distance to the target day, the latest one will be used. For procedures planned on Visit 2, if it is done on the same date as the first IMP injection but the performance time is missing, it will belong to Visit 2 time window.

Table 8 - Time window for pharmacokinetics/pharmacodynamics variables

Visit	Target day	Time windows for						
		FeNO post-Bronchodilator	Serum dupilumab concentration	Anti-drug antibodies	Total IgE	PARC	Eotaxin-3	Fibrinogen
Visit 1 (Week -4±1)	-28±7							
Visit 2 (Week 0)	1	1-	1-	1-	1-	1-	1-	1-
Visit 3 (Week 2)	15		1*-21					
Visit 4 (Week 4)	29	1*-42	22-42				1*-56	
Visit 5 (Week 8)	57	43-70	43-70					
Visit 6 (Week 12)	85	71-126	71-126	1*-126	1*-224		57-126	
Visit 7 (Week 16)	113							
Visit 8 (Week 20)	141							
Visit 9 (Week 24)	169	127-210	127-210	127-266		127-266		1*-266
Visit 10 (Week 28)	197							
Visit 11 (Week 32)	225							
Visit 12 (Week 36)	253	211-308	211-308					
Visit 13 (Week 40)	281							
Visit 14 (Week 44)	309							
Visit 15 (Week 48)	337							

Visit	Target day	Time windows for						
		FeNO post-Bronchodilator	Serum dupilumab concentration	Anti-drug antibodies	Total IgE	PARC	Eotaxin-3	Fibrinogen
Visit 16 (Week 52)	365	309-406	309-406	267-406	225-406	1 ⁺ -406	267-406	267-406
Visit 17 (Week 56)	393							
Visit 18 (Week 60)	421							
Visit 19 (Week 64)	449	>406	>406	>406	>406	>406	>406	>406

1-: up to 1st dose date/time or randomization if patient is not treated;

1+: after 1st dose date/time or randomization date if patient is not treated;

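### The more-than-84-day rule for persistent ADA falls exactly on two of the three post-baseline sampling gaps, so on-schedule positives at Weeks 52 and 64 are classed as transient

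*SAP*

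**What the plan says.** SAP 2.1.5 gives ADA status "at Visit 2 (Day 1), Week 12, Week 24, Week 52 and follow up at Week 64 will be provided". It then splits treatment-emergent responses into three classes:

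- *Persistent*: a response "with two or more consecutive ADA positive sampling time points, separated by greater than" a "12-week period (84 days), with no ADA negative samples in between". A greater-than sign in the text confirms that the inequality is strict.
- *Indeterminate*: "defined as a treatment-emergent response with only the last collected sample positive in the ADA assay".
- *Transient*: "defined as a treatment-emergent response that is not considered persistent OR indeterminate", that is, the residual class.

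The same rules are repeated for an on-treatment version in which "only on-treatment measurements (measurements during the treatment epoch) are considered post first dose".

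SAP Table 8 ("Time window for pharmacokinetics/pharmacodynamics variables") sets the target days: 85 for Week 12, 169 for Week 24, 365 for Week 52 and 449 for Week 64. Protocol 1.3.1 (footnote a) allows visits to vary by ±"3 days for the randomized IMP treatment period and ±5 days for the post IMP treatment period". The SAP does not say whether the separation is counted on actual sampling dates or on nominal visit days.

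SAP 2.4.6.1.2 tabulates each class, summarizes peak titer by class, and plans plots of dupilumab concentration by ADA classification. It names the three classes among the variables that may be explored against PK and efficacy.

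**The concern.** A strict limit of 84 days, set against a schedule with two gaps of exactly 84 days, leaves no margin. A patient sampled on the planned days and positive at both ends of such a gap misses the persistent class by one day, and the residual definition then makes the response transient.

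The result is hardest to defend at the end of the study. Positives at Weeks 52 and 64 are stronger evidence of a lasting response than a single positive at Week 64. Yet the first patient is labelled as having a response that went away, and the second as undecided. By-class tables and concentration plots built on such labels would partly describe the visit calendar rather than the immune response.

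**Working it through.** **Plan's own figure.** 12 weeks × 7 = 84 days, as the SAP states.

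**Nominal gaps (Table 8 target days).**
- Week 12 to 24: 169 − 85 = 84 days
- Week 24 to 52: 365 − 169 = 196 days
- Week 52 to 64: 449 − 365 = 84 days

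Day 1 to Week 12 is also 84 days but plays no part, because a treatment-emergent response requires a negative or missing baseline.

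**Gaps inside the protocol windows.** ±3 days applies at Weeks 12, 24 and 52, and ±5 days at Week 64.
- Weeks 12–24: 84 − 6 to 84 + 6 = 78 to 90 days
- Weeks 24–52: 196 − 6 to 196 + 6 = 190 to 202 days
- Weeks 52–64: 84 − 8 to 84 + 8 = 76 to 92 days

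**All patterns for a patient with four post-baseline samples (2⁴ = 16).** Each pattern was classified at the target days and at every in-window combination of days.

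| Result | Patterns (weeks positive) | Number |
|---|---|---|
| Always persistent | 24+52; 12+24+52; 24+52+64; all four | 4 |
| Transient at target days, persistent or transient by timing | 12+24; 12+24+64; 52+64; 12+52+64 | 4 |
| Always transient | 12; 24; 52; 12+52; 12+64; 24+64 | 6 |
| Always indeterminate | 64 | 1 |
| No positive | none | 1 |

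In the on-treatment version (Weeks 12, 24, 52) only 12+24 changes class with timing.

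**Chance of exceeding 84 days on actual dates.** Assumption: each allowed day is equally likely and visits are independent. The gap is 84 + d₂ − d₁, where d₁ and d₂ are the deviations from target.
- Weeks 12–24: 7 × 7 = 49 combinations, 7 with gap exactly 84; (49 − 7)/2 = 21 exceed it, 21/49 = 42.9%.
- Weeks 52–64: 7 × 11 = 77 combinations, 7 with gap exactly 84; (77 − 7)/2 = 35 exceed it, 35/77 = 45.5%.

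**Would changing the sign be enough?** With at least 84 days on actual dates, the shares become (21 + 7)/49 = 57.1% and (35 + 7)/77 = 54.5%. Timing would still decide.

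**On nominal days.** Timing plays no part, but 84 is never more than 84. All four patterns in the second row are then transient with certainty, including 52+64.

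**The case against.** The strongest reply is that the problem is narrow and partly a matter of preference. Much of that stands.

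- A reader might infer that more than half of all patients positive at Weeks 12 and 24, or at Weeks 52 and 64, are mislabelled. The documents do not support this. Anyone whose run includes both Weeks 24 and 52 is persistent whatever the timing, because that gap is at least 190 days. The percentages apply only to the four patterns above. The documents do not say how common these are, and they do not support the uniform-timing assumption either.
- A reader might also infer that visit timing certainly decides the class. The SAP leaves the date basis open. If nominal days are intended, the rule is deterministic, though the Week 52+64 result is then always wrong.
- It might seem that the ADA incidence objective or the safety associations are compromised. Treatment-emergent incidence is defined before this split and does not change. The variables listed for the safety associations in SAP 2.4.6.1.2 do not include the three classes. Protocol 9.4.3 (Table 11) names treatment-emergent incidence, titers and neutralizing status, not persistence.
- For positives at Weeks 12 and 24 followed by negatives at Weeks 52 and 64, transient is a reasonable label. The case against the rule there is inconsistency on actual dates, not an evident error.
- Under the reduced schedule (protocol 1.3.2), patients who stop treatment early have no Week 64 ADA sample, so the Week 52+64 case does not arise for them.

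None of this answers the case of a patient negative at Week 24 and positive at both Weeks 52 and 64.

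**Conclusion.** The point holds as a minor defect in a derivation rule. It follows directly from the SAP's definitions and target days: four of 16 patterns are transient on schedule. On actual dates they become persistent in 42.9% (Weeks 12–24) or 45.5% (Weeks 52–64) of in-window timings, if timing is uniform and independent; on nominal days they never do. The collision of the 84-day limit with the 84-day gaps needs no assumption.

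The firm error is the end-of-study one. A response positive at both of the last two samples is called transient with no sample showing resolution, while a single positive at Week 64 is called indeterminate. At target days the rule moves responses only from persistent to transient, so persistence is understated.

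The reach is limited to descriptive by-class counts, titer summaries and concentration plots, and to associations with PK and efficacy that may be explored. No primary or key secondary test depends on it.

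**What to change.** Amend SAP 2.1.5 and the ADA derivation, for both the overall and the on-treatment version:

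1. Define the separation by nominal visit as at least 12 weeks, with no negative sample in between.
2. State that a response still positive at the last collected sample is not classed as transient, and name its class when it does not meet the persistent rule. Indeterminate is the natural choice.
3. State how ADA samples without a nominal visit enter the rule: the early-discontinuation sample (protocol 1.3.2) and additional samples after early discontinuation or an adverse event (protocol 7.1.1 and 8.5.3). Table 8 assigns values to visit windows for by-visit summaries, but the SAP does not say whether that assignment also feeds the response classes.

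The cost is a few lines of SAP text and programming, with no change to data collection. There is a downside. On the planned schedule every pair of consecutive post-baseline visits is at least 12 weeks apart, so any two consecutive planned positives become persistent, including Weeks 12+24 followed by negatives. Persistent patterns rise from 4 at target days to 4 + 4 = 8. Under item 2, 12+64 and 24+64 also leave the transient class. The persistent count may therefore rise and would not be comparable with counts made under the current definition; the report should say so.

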2.1.6 Pharmacodynamic/genomics endpoints

Whole blood biomarkers blood eosinophil and neutrophil counts will be measured as part of the standard 5-part WBC differential cell count on a hematology auto analyzer.

For plasma/serum biomarkers, Eotaxin-3 will be assayed at Visit 2 (Week 0), Visit 4 (Week 4), Visit 6 (Week 12), Visit 9 (Week 24), Visit 16 (Week 52) and Visit 19 (Week 64); total IgE will be assayed at Visit 2 (Week 0), Visit 6 (Week 12), Visit 16 (Week 52) and Visit 19 (Week 64); Pulmonary and Activation-Regulated Chemokine [PARC] will be assayed at Visit 2 (Week 0), Visit 16 (Week 52) and Visit 19 (Week 64); Fibrinogen will be assayed at Visit 2 (Week 0), Visit 9 (Week 24), Visit 16 (Week 52) and Visit 19 (Week 64).

Fractional exhaled nitric oxide (FeNO; postbronchodilator) will be analyzed using a NIOX instrument (Aerocrine AB, Solna, Sweden), or similar analyzer using a flow rate of 50 mL/s, and reported in parts per billion (ppb). This assessment should be conducted prior to spirometry and following a fast of at least 1 hour at Visit 2 (Week 0), Visit 4 (Week 4), Visit 5 (Week 8), Visit 6 (Week 12), Visit 9 (Week 24), Visit 12 (Week 36), Visit 16 (Week 52) and Visit 19 (Week 64).

Pharmacogenetic testing is optional and voluntary. A separate written informed consent form must be signed before sampling. For those patients who signed the optional pharmacogenetic informed consent form, blood samples for exploratory genetic analysis of DNA or RNA will be collected at the study visit as specified in the study flow chart, and these samples will be stored for future analysis.

2.1.7 Health Related Quality-of-life endpoints

2.1.7.1 *The 5-level Euro Quality of Life-5 Dimension questionnaire (EQ-5D-5L)*

The 5-level Euro Quality of Life-5 Dimension questionnaire (EQ-5D-5L) ([Appendix E](#)) is a standardized HRQoL questionnaire developed by the EuroQol Group in order to provide a simple, generic measure of health for clinical and economic appraisal ([8](#)). EQ-5D is designed for self-completion by patients.

The EQ-5D essentially consists of 2 pages: the EQ-5D descriptive system and the EQ VAS. The EQ-5D comprises 5 dimensions: mobility, self-care, usual activities, pain/discomfort and anxiety/depression. Each dimension has 5 levels: no problems, slight problems, moderate problems, severe problems, and extreme problems. EQ-5D-5L health status will be converted into a single index value by using EQ-5D-5L value sets based on UK population. The EQ VAS records the respondent's self-rated health on a vertical VAS. The EQ VAS 'thermometer' has endpoints of 100 (best imaginable health state) at the top and 0 (worst imaginable health state) at the bottom. EQ-5D self-reported VAS data generates information on the self-perceived overall health-related quality of life.

EQ-5D will be assessed at Visit 2 (Week 0), Visit 9 (Week 24), and Visit 16 (Week 52).

2.1.8 Health economic endpoints

A questionnaire of health care resource utilization (collection of sick days, lost usual activities, and additional physician visits or other health care utilization) will be administered at Visit 2 (Week 0), Visit 4 (Week 4), Visit 5 (Week 8), Visit 6 (Week 12), Visit 7 (Week 16), Visit 8 (Week 20), Visit 9 (Week 24), Visit 10 (Week 28), Visit 11 (Week 32), Visit 12 (Week 36),

Visit 13 (Week 40), Visit 14 (Week 44), Visit 15 (Week 48), Visit 16 (Week 52) and Visit 19 (Week 64).

2.2 DISPOSITION OF PATIENTS

This section describes patient disposition for both patient study status and the patient analysis populations.

Screened patients are defined as any patients who signed the informed consent.

Randomized patients consist of all patients with a signed informed consent form who have had a treatment kit number allocated and recorded in the IRT database, regardless of whether the treatment kit was used.

For patient study status, the total number of patients in each of the following categories will be presented in the clinical study report using a flowchart diagram or summary table:

- Screened patients
- Screen failure patients and reasons for screen failure
- Nonrandomized but treated patients
- Randomized patients
- Randomized but not treated patients
- Randomized and treated patients
- Patients who did not complete treatment as per protocol
- Patients who discontinued study treatment by main reason for permanent treatment discontinuation including due to the COVID-19 pandemic
- Patients who withdraw from study
- Patients who withdraw from study prior to Week 52
- Patients who withdraw from study prior to Week 52 by main reason for study discontinuation including due to the COVID-19 pandemic
- Patients who withdraw from study by main reason for study discontinuation including due to the COVID-19 pandemic
- Vital status at last study contact

For all categories of patients (except for the screened and nonrandomized categories) percentages will be calculated using the number of randomized patients as the denominator. Reasons for treatment discontinuation will be supplied in tables giving numbers and percentages by treatment group. This summary will be provided by treatment group.

All critical or major deviations related to randomization procedures will be summarized in tables giving numbers and percentages of deviations by treatment group.

Additionally, efficacy populations will be summarized by number of patients on the randomized population.

- Efficacy population: intent-to-treat (ITT) population defined in [Section 2.3](#)

The analysis populations for safety defined in [Section 2.3](#) pharmacokinetics/pharmacodynamics (PK/PD) will be summarized by number of patients on the safety population.

- Safety population
- PK population
- ADA population

